1. Study Title

Association of the $\text{PaO}_2/\text{PaCO}_2$ Ratio With ICU Mortality Independent of Oxygen Saturation and Mean Arterial Pressure: A MIMIC-II Retrospective Cohort Study

Acronym: RATIO-MIMIC

2. Study Objectives

Primary Objective:

- To determine whether the $\text{PaO}_2/\text{PaCO}_2$ ratio is independently associated with ICU mortality in critically ill adults, adjusting for oxygen saturation (SpO_2) and mean arterial pressure (MAP).

Secondary Objectives:

- To explore the relationship between $\text{PaO}_2/\text{PaCO}_2$ ratio categories (e.g., tertiles or quartiles) and ICU length of stay.
- To perform subgroup analyses by mechanical ventilation status, age, or primary ICU diagnosis.

3. Study Design

- **Type:** Observational
- **Design:** Retrospective cohort study
- **Population:** Adult ICU patients (≥ 18 years) in MIMIC-II database
- **Sampling Method:** Retrospective census of all eligible patients meeting inclusion/exclusion criteria
- **Cohorts/Groups:** Single cohort; exposure analyzed as continuous and categorical (quartiles or tertiles)
- **Time Frame:** ICU admissions from 2001–2008 (MIMIC-II database)

4. Study Population

Inclusion Criteria:

1. Adult patients (≥ 18 years) at ICU admission
2. First (index) ICU admission during hospitalization

3. At least one arterial blood gas measurement with PaO_2 and PaCO_2
4. Available SpO_2 and MAP during ICU stay
5. Documented ICU discharge status

- **Exclusion Criteria:**
 1. Age <18 years
 2. Missing or non-numeric PaO_2 or PaCO_2 values
 3. Missing ICU outcome data
 4. Physiologically implausible ABG values
 5. ECMO during ABG measurement (if identifiable)
 6. No SpO_2 or MAP measurements during ICU stay
 7. Repeat ICU admissions beyond index stay
 8. DNR/comfort-care orders prior to ABG measurement (optional for sensitivity analyses)

5. Data Collection and Variables

- **Exposure Variable:** $\text{PaO}_2/\text{PaCO}_2$ ratio (calculated from ABG measurements)
- **Outcome Variable:** ICU mortality (yes/no)
- **Covariates for Adjustment:**
 - Oxygen saturation (SpO_2)
 - Mean arterial pressure (MAP)
 - Age, sex, ICU type (medical/surgical), comorbidities (if available)
 - Mechanical ventilation status
- **Time Points:** First ABG per ICU stay (primary), or median/peak ABG values for sensitivity analysis

6. Statistical Analysis Plan (SAP)

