6.2 Primary Analysis

- **Model:** Multivariable logistic regression
- **Dependent Variable:** ICU mortality (binary)
- **Independent Variable:** $\text{PaO}_2/\text{PaCO}_2$ ratio (continuous or categorical)
- **Covariates:** SpO_2 , MAP, age, sex, ICU type, comorbidities
- **Effect Measures:** Adjusted odds ratios (ORs) with 95% confidence intervals
- **Assessment of Independence:** Evaluate whether $\text{PaO}_2/\text{PaCO}_2$ remains statistically significant after adjustment

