6.5 Statistical Software

- R (version ≥ 4.0) or STATA (version ≥ 16)
- Two-sided p-value <0.05 considered statistically significant

7. Ethical Considerations

- Secondary analysis of **de-identified public data (MIMIC-II)**
- No new patient consent required
- Approved by MIT and Beth Israel Deaconess Medical Center Institutional Review Boards for public data use

8. Reporting

- Follow **STROBE guidelines** for observational studies
- Present baseline tables, regression results, and flowchart of included/excluded patients
- Include sensitivity and subgroup analyses
- Report odds ratios, 95% CI, and p-values

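### Adjusting only for SpO2 cannot by itself support a claim of independence from oxygen saturation; the 6.2 significance rule can exceed 5%, by an amount the documents do not fix

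*Combined protocol and SAP*

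**What the plan says.** The title (section 1) claims an association with "ICU Mortality Independent of Oxygen Saturation and Mean Arterial Pressure". The primary objective (section 2) is narrower: it describes the adjustment variable as "oxygen saturation (SpO_2", and section 5 lists the same variable.

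The primary analysis (6.2) is "Multivariable logistic regression" of ICU death on the ratio, entered as continuous or categorical, with covariates "SpO_2 , MAP, age, sex, ICU type, comorbidities". No functional form is given for SpO2. Independence is assessed by whether the ratio "remains statistically significant after adjustment", and 6.5 sets the threshold: "Two-sided p-value <0.05 considered statistically significant".

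The exposure comes from the first gas in the primary analysis: "First ABG per ICU stay (primary), or median/peak ABG values for sensitivity analysis". For SpO2 the only requirement is "Available SpO_2 and MAP during ICU stay"; no rule says which reading enters the model. Arterial saturation is not listed as a covariate. The sensitivity analyses in 6.3 vary the blood-gas values and the DNR exclusion. Section 6.4 deals with absent covariates, not inexact ones.

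**The concern.** PaO2 is the numerator of the exposure and largely determines true arterial saturation. A pulse oximeter reads that saturation with error. Both statements are general physiology and measurement knowledge, not taken from the documents. Adjusting for a noisy version of a confounder removes only part of it. What is left stays correlated with the ratio, because PaO2 carries information on the same saturation that the oximeter misses. The 6.2 rule would read that residue as independence.

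This is bias rather than sampling noise, so more patients do not remove it. They make the test more certain to detect it, and the design takes every eligible patient. At stake are the title claim and the primary conclusion, and no planned analysis would show the problem.

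**Working it through.** **What can be reproduced.** The only design figure is the nominal two-sided 0.05. No sample size, event count, mortality or effect size is stated, so the actual error rate cannot be derived from the documents. The check is a simulation under the null that the ratio adds nothing beyond true saturation.

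**Inputs from the plan.** Logistic regression; a continuous ratio from one gas; SpO2 and MAP as covariates; two-sided 5% test of the ratio.

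**Assumed inputs, none in the documents.**
- PaO2 log-normal, median 90 with log-SD 0.35, or median 120 with log-SD 0.55. PaCO2 log-normal, median 40, log-SD 0.22, with no effect on death.
- True saturation computed from PaO2 by the standard dissociation-curve formula.
- SpO2 = true saturation + normal error, rounded and capped at 100.
- Death depends only on true saturation, MAP and age, with mortality 12% at average covariates. The odds ratio (OR) per 1-point fall in saturation is 1.00, 1.03, 1.06 or 1.10; the last three are log-odds of about 0.03, 0.06 and 0.095.
- Fitted model: death on untransformed ratio, linear SpO2, MAP and age. Sex, ICU type and comorbidities were left out.

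**Benchmark.** With error SD 0, or with no saturation effect, rejection was 3.0–6.5% across cells. With 200 replicates, the fewest used, the simulation standard error at 5% is √(0.05×0.95/200) = 1.5 points, so this is nominal.

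**Rejection of a ratio that adds nothing (%), for OR 1.03 / 1.06 / 1.10 per point:**

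| N | Error SD | PaO2 median 90 | PaO2 median 120 |
|---|---|---|---|
| 1,000 | 2 | 6.2 / 3.8 / 8.2 | 4.2 / 6.0 / 5.5 |
| 1,000 | 3 | 5.5 / 6.2 / 13.5 | 4.5 / 7.8 / 8.8 |
| 5,000 | 2 | 6.5 / 8.8 / 19.8 | 6.8 / 6.5 / 11.5 |
| 5,000 | 3 | 7.5 / 23.0 / 56.2 | 6.8 / 12.5 / 30.5 |
| 15,000 | 2 | 13.0 / 24.0 / 49.0 | 9.5 / 11.5 / 29.5 |
| 15,000 | 3 | 16.0 / 52.5 / 94.5 | 12.5 / 26.5 / 66.5 |

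The central cells (N=5,000, SD 3, OR 1.06), rerun with 2,000 replicates, gave 22.6% and 13.6%. With true saturation in place of SpO2 the same cells gave 5.2% and 5.1%, so the excess comes from the error in SpO2.

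**Bias, not noise.** In the median-90 setting at SD 3 and OR 1.06, the spurious OR per SD of the ratio was 0.940, 0.937 and 0.940 at N=1,000, 5,000 and 15,000. It does not move towards 1; only the rejection rate grows.

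**Second run.** A separate simulation with an untransformed ratio, linear SpO2, error SD 2–3 and log-odds 0.03–0.10 gave 4–10%, 4–37% and 4–79% at the same three sizes. The upper ends fall between the two PaO2 settings in the table (8.8–13.5, 30.5–56.2 and 66.5–94.5). The low ends of 4% are within simulation error of 5%.

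**Effect of averaging.** In that run, averaging SpO2 readings before the gas lowered rejection from 37% to 11% at N=5,000, SD 3 and log-odds 0.10. Averaging reduces the excess but does not remove it, and it cannot correct an error that persists across a patient's readings.

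**The case against.** **The objective already says SpO2.** If the question is whether the ratio adds to a bedside SpO2 reading, a ratio that carries what the oximeter misses is a true positive, and 5% is not the right benchmark. This stands for the objective. It does not rescue the title, which drops the qualifier, or the 6.2 rule, which turns significance into independence.

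**The size is assumed.** A reader might infer that the 6.2 test rejects far above 5% as a matter of fact. The documents do not support that. At N=1,000 with error of 2 to 3 points most cells are near nominal, and without a saturation effect there is no inflation. Higher rates arise with the logarithm of the ratio and a flexible SpO2 term: 35–44% at SD 2 and 77–82% at SD 3, for N=5,000 and log-odds 0.10. The plan specifies neither of these. They also show that modelling SpO2 flexibly does not cure the problem.

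**The obvious remedy is partly circular.** Saturation computed from PaO2 is a function of the exposure's numerator. Adjusting for it leaves the ratio to be tested largely through PaCO2 and the range where saturation is flat, which changes the question. The return to 5% in the simulation is also built in, because saturation was generated from PaO2. This stands; computed saturation should not be the main fix. Nor do the documents show that measured arterial saturation is recorded, or give an error variance for a correction method.

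**Effect sizes will be reported.** ORs with confidence intervals are planned, so a spurious OR of 0.94 would look small. That helps a careful reader, but the stated rule for independence is significance, not size.

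**Conclusion.** The concern holds in conditional form. The title's claim goes further than adjustment for SpO2 can support. If saturation predicts death, the 6.2 rule can reject above 5% for a ratio that adds nothing beyond true saturation, and the excess grows with cohort size.

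Under the plainest reading of 6.2, the assumed range is about 4–10% at N=1,000, 4–37% at N=5,000 and 4–79% at N=15,000. The upper ends move with the assumed PaO2 spread, as the table shows, as well as with SpO2 error, effect strength and model form. None of these is in the documents, so no single figure should be quoted as the trial's error rate. Nor does the check show that a positive result would be false: a real contribution of the ratio remains possible, and the planned analysis could not tell the two apart.

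**What to change.** - **6.2:** use as the covariate the mean of the SpO2 readings in a set window up to the index gas, and state the window.
- **6.3:** add a sensitivity model with measured arterial saturation from the same gas, where recorded, and report how many patients have it. Add a SIMEX or regression-calibration analysis over an assumed SpO2 error SD of 1 to 3 points; a range is needed because the documents give no error variance.
- **Claim:** use *independent of oxygen saturation* only if the ratio survives these analyses, with survival defined in advance. Otherwise conclude *after adjustment for SpO2*, which matches the primary objective, and align the title.
- **Not as the main fix:** saturation computed from PaO2, for the reason given above.

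The cost is SAP wording, a few extra models on the same data, a wider interval for the ratio and possibly a narrower claim.

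### MAP is the only haemodynamic covariate, so residual confounding by shock may stay in the ratio OR and be counted as independence

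*Combined protocol and SAP*

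**What the plan says.** The title claims an association "Independent of Oxygen Saturation and Mean Arterial Pressure", and the primary objective in Section 2 repeats that aim with the same two adjustment variables.

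- **Eligibility (Section 4):** the requirement is "Available SpO_2 and MAP during ICU stay". No time point or summary (first, lowest, mean) is fixed.
- **Timing (Section 5):** the time-point line covers the blood gas only: "First ABG per ICU stay (primary), or median/peak ABG values for sensitivity analysis". MAP is listed by name, with no matching time.
- **Primary model (Section 6.2):** the covariates are "SpO_2 , MAP, age, sex, ICU type, comorbidities". Independence is judged by whether the ratio "remains statistically significant after adjustment"; Section 6.5 sets two-sided 0.05.
- **Subgroup and sensitivity analyses (Section 6.3):** none concerns vasopressor use or shock.

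No vasopressor, inotrope, lactate, shock or severity-score variable appears among the covariates, exclusions, subgroups or sensitivity analyses. The plan gives no sample size, event rate or effect size.

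**The concern.** In intensive care, MAP is a treated quantity. One recorded value can belong to a patient with no support or to one whose pressure is held up by an infusion, and their risks of death may differ widely. A single MAP term gives both the same adjustment. Because MAP may come from any time in the stay, it may also reflect treatment begun after the blood gas that defines the exposure.

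Shock can also move the exposure, by lowering PaCO2 through hyperventilation or PaO2 through lung injury. If shock is related to the ratio after the listed covariates are taken into account, it stays in the ratio OR. A significant ratio would then pass the Section 6.2 rule for a reason unrelated to the ratio, and no planned analysis would show it.

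**Working it through.** There is no figure in the plan to reproduce. Every input below is an assumption, chosen to show what could happen.

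**A. One binary confounder, no true ratio effect, MAP equal in all patients.** Assumed: share *p* on vasopressors 0.2 or 0.3; mortality 25% on and 10% off; ratio lower by *d* = 0.3 or 0.5 SD in those on vasopressors. With unit variance, approximately

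ln OR per SD ≈ −*d* × (share on vasopressors among deaths − share among survivors)

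- *p* = 0.2: overall mortality *m* = 0.2×0.25 + 0.8×0.10 = 0.13. Shares: 0.05/0.13 = 0.385 and 0.15/0.87 = 0.172; difference 0.212.
- *p* = 0.3: *m* = 0.075 + 0.07 = 0.145. Shares: 0.075/0.145 = 0.517 and 0.225/0.855 = 0.263; difference 0.254.

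With z ≈ |ln OR| × √(N·m·(1−m)):

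| *p* | *d* | OR by formula | OR by simulation (400,000 patients) | z (formula OR), N = 10,000 | z, N = 5,000 |
|---|---|---|---|---|---|
| 0.2 | 0.3 | 0.938 | 0.937 | 2.1 | 1.5 |
| 0.2 | 0.5 | 0.899 | 0.906 | 3.6 | 2.5 |
| 0.3 | 0.3 | 0.927 | 0.931 | 2.7 | 1.9 |
| 0.3 | 0.5 | 0.881 | 0.881 | 4.5 | 3.2 |

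If the ratio is higher in shock, the simulated ORs invert to about 1.07 to 1.14. At an assumed 10,000 patients all four cases exceed 1.96; at 5,000 the two with *d* = 0.3 do not. Adding the vasopressor indicator returns the OR to 0.99–1.00, but only because here the indicator is the whole confounder.

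**B. Latent shock severity, with treatment raising MAP (200,000 patients per scenario, no true ratio effect).** Assumed: severity S is standard normal and raises the log-odds of death by 0.8 per SD (mortality about 9.5%). Untreated MAP is 78 − 10·S with noise SD 8. Patients below 65 (about 15%) are treated, and treatment closes 0% or 90% of their gap to 75. Rejection rates are scaled to an assumed N of 5,000.

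| Ratio–S correlation | MAP only, 0% restored | MAP only, 90% restored | + indicator (90%) | + indicator and intensity (90%) | Rejection, MAP only → indicator and intensity (90%) |
|---|---|---|---|---|---|
| 0 | 1.003 | 0.992 | 0.994 | 0.994 | 5% → 5% |
| −0.1 | 0.951 | 0.970 | 0.982 | 0.984 | 10% → 6% |
| −0.2 | 0.939 | 0.917 | 0.940 | 0.946 | 42% → 20% |
| −0.3 | 0.911 | 0.865 | 0.897 | 0.904 | 83% → 52% |

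Monte Carlo error in each OR is about 0.01. With 90% restoration, patients with recorded MAP 70–80 had mortality of about 19% if treated and 9.5% if untreated.

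Share of the log-OR bias removed by a yes/no indicator: at −0.2, 1 − ln(0.940)/ln(0.917) = 1 − 0.0619/0.0866 = 29%; at −0.3, 1 − 0.1087/0.1450 = 25%. Adding intensity raises these to 36% (1 − 0.0555/0.0866) and 30% (1 − 0.1009/0.1450).

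**The case against.** - **The plan claims less than a reader may infer.** One might read the title as claiming independence from shock or haemodynamic status. The documents do not say so: they name SpO2 and MAP, and that literal statement can be met. They also do not say that MAP is treated as an unsupported value; they only list it. This stands, and it limits the point to what the OR can be taken to show.
- **The direction is unknown and the bias may be nil.** Lower PaCO2 raises the ratio and lower PaO2 reduces it, so the two routes could cancel. In calculation A with a quarter of patients on vasopressors, a 0.1 SD shift gave an OR of about 0.97 and no shift gave 1.00. This stands.
- **The listed covariates are left out of both calculations.** SpO2 should take up part of the PaO2 route. In an extreme case with the shift passing wholly through SpO2, crude ORs of 0.96 and 0.95 returned to 1.00 after SpO2 adjustment. The assumed shift must therefore be what remains after all listed covariates, and nothing in the documents supports a particular size. Against this, comorbidities are included only if available, and ventilation status, listed in Section 5, is absent from the Section 6.2 model.
- **Masking by vasopressors is only part of the problem.** In calculation B most of the bias at −0.2 and −0.3 is already there with no restoration of MAP, because MAP marks shock imperfectly even when untreated. At −0.1 the effect of treatment cannot be told from simulation error.
- **A yes/no indicator is a partial remedy.** Calculation B agrees. This argues for limiting the conclusion as well as adding the covariate.

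**Conclusion.** The point holds in a bounded form. The model cannot separate a vasopressor-supported pressure from an unsupported one, so confounding by shock may remain in the adjusted ratio OR, and the Section 6.2 significance rule would count it as independence.

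Size and direction cannot be determined from the documents. The ORs of about 0.88 to 0.94 per SD, or their inverses, and the rejection rates are illustrations. They rest on assumed prevalence, mortality, ratio–shock relation and cohort size, and they omit SpO2 and the other listed covariates. With no relation between ratio and shock given those covariates, there is no bias. It would be wrong to infer that a significant ratio must be shock in disguise, or that adding a vasopressor term would establish haemodynamic independence. This is a cheap improvement to an observational plan; it does not correct a contradiction in it.

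**What to change.** 1. In Sections 5 and 6.2, define MAP as a value at or before the index blood gas, and state which value is used.
2. Add vasopressor or inotrope use at that time as a covariate (yes/no, with dose if recorded). Report the ratio OR with and without it. A MAP-by-vasopressor term is optional, as a sensitivity analysis in Section 6.3.
3. State that this reduces but does not remove confounding by shock.
4. Word the conclusion as *after adjustment for recorded MAP and vasopressor use*, not as independence from haemodynamic status.
5. The documents do not say whether the database holds infusion data. If it cannot be extracted, use only the limited wording, *after adjustment for recorded MAP*.

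Cost: some extraction work, one or two model terms, and a conclusion that may become less favourable. The data are retrospective, so nothing changes for patients.

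### The index ICU stay is tied to the hospitalization, so the plan does not clearly hold the cohort to one row per patient and makes no provision for repeated patients in the primary logistic model

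*Combined protocol and SAP*

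**What the plan says.** Four parts of the combined protocol and SAP decide what one row of the analysis file is.

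- Section 4, inclusion criterion 2: "First (index) ICU admission during hospitalization". The reference unit is the hospitalization.
- Section 4, exclusion criterion 7: "Repeat ICU admissions beyond index stay". It reuses the term index stay and states no unit of its own.
- Section 3: the sampling method is a "Retrospective census of all eligible patients meeting inclusion/exclusion criteria", over an admission window of 2001 to 2008.
- Section 5: the exposure is taken once per ICU stay, "First ABG per ICU stay (primary), or median/peak ABG values for sensitivity analysis".

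Section 6.2 names "Multivariable logistic regression" and reports "Adjusted odds ratios (ORs) with 95% confidence intervals". It judges independence by whether the ratio stays significant after adjustment, and Section 6.5 sets the threshold at a two-sided 0.05. Section 6.2 mentions no clustering, GEE or random effect. The sensitivity analyses in Section 6.3 deal with extreme blood gas values, DNR or comfort-care patients and the choice of blood gas. None of them restricts the cohort to one stay per patient.

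**The concern.** With an eight-year window, one patient can have several hospitalizations. If the index stay is counted within each, each brings its own eligible row, and two programmers working from this text could build different cohorts.

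Repetition also depends on the outcome, because only a patient who leaves the ICU alive can come back. Suppose patients with a low ratio return more often, their ratio stays similar from stay to stay, and an unmeasured frailty affects death. The low-ratio rows then gain extra stays from patients already selected for surviving. Mortality at that end of the scale falls for a reason unrelated to the ratio. The plan's decision about independence rests on one p-value, and in a large database a small shift of this kind can be enough to cross 0.05.

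**Working it through.** The documents state no sample size, event count or re-hospitalization rate, so there is no figure to reproduce. The first step is a reading of the text. The others use assumed inputs.

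**1. What counts as a row.** Take a patient with three hospitalizations, each with an eligible ICU stay, who survives the first two stays and dies in the third.

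| Reading | Rows | Survivor rows | Death rows |
|---|---|---|---|
| Index stay per hospitalization (literal inclusion 2) | 3 | 2 | 1 |
| Index stay per patient (possible reading of exclusion 7) | 1 | 1 | 0 |

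The two readings give different data and a different outcome for the same patient.

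**2. Variance alone.** Let a share q of patients have two stays and the rest one, with intra-patient correlation ρ. The design effect is DE = 1 + ρ(Σm²/Σm − 1), and the actual two-sided level is 2[1 − Φ(1.96/√DE)].

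- q = 0.15, ρ = 0.2: Σm²/Σm = (0.85 + 0.15×4)/1.15 = 1.261. DE = 1 + 0.2×0.261 = 1.052, and the level is 0.056.
- q = 0.30, ρ = 0.5: Σm²/Σm = (0.70 + 0.30×4)/1.30 = 1.462. DE = 1 + 0.5×0.462 = 1.231, and the level is 0.077.
- Across q = 0.05 to 0.30 and ρ = 0.05 to 0.5, the level runs from 0.0505 to 0.0773.

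This formula ignores the fact that death ends the sequence, which limits outcome clustering. It also says nothing about selection.

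**3. With a true effect.** Simulation of 8,000 patients, 150 runs per setting, up to 6 stays with death terminal, conditional log OR −0.3 per SD, and first-stay mortality 10–17%. Within-patient exposure correlation was 0 to 0.8 and frailty SD 0 to 1.5.

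| Re-hospitalization probability | Rows per patient | Difference in OR, all stays v. first stay |
|---|---|---|
| 5% or 15% | 1.05 to about 1.17 | at most 0.007 |
| 30% | about 1.34 to 1.38 | 0.002 to 0.019 |

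The largest gap is 0.792 against 0.811. That is 0.811/0.792 = 1.024, and ln 0.811/ln 0.792 = 0.2095/0.2332 = 0.90, so the log OR is attenuated by about 10%. The ratio of naive to cluster-robust standard error was 0.995–1.005 throughout.

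**4. With no effect.** Simulation of 15,000 patients with about 1.2–1.4 rows each; rejection rate at p<0.05.

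| Assumed setting | Rejection rate |
|---|---|
| Return unrelated to the ratio | 4.5–8% |
| Return depends on the ratio, most settings | 5–9% |
| Strong dependence, frailty SD 1.5, no covariate carrying frailty | 16–30% |
| First stay per patient | about 4–7.5% |

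The OR moved by at most about 3%.

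**5. What changes the answer.** These null settings used 200 runs each, so the Monte Carlo standard error at 5% is √(0.05×0.95/200) = 1.5 points.

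- *Covariates.* With 15,000 patients, frailty SD 1.5, 20% baseline re-hospitalization and a return log-odds of −0.6 per SD of the ratio, the rejection rate was 14% (OR 1.016). When a covariate captured half the frailty variance, it was 7.5% (OR 1.010).
- *Sample size.* With 5,000 patients the same pair was 11% and 3.5%.
- *Frail patients also returning more often.* This offsets the selection; rates were 4–13%.
- *Clustered errors.* Where return depended on the ratio but not on frailty, naive and cluster-robust tests rejected almost equally often: 6–20% for both at frailty SD 1.0, and 14–47% against 14–46% at SD 1.5. Clustering corrects variance and leaves the selection in place.

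**The case against.** The strongest reply is that eligibility criteria apply cumulatively. Exclusion 7 carries no per-hospitalization limit, so it can narrow inclusion 2 to one stay per patient. Sections 3, 6.4 and 8 all speak of patients. This stands to the extent that the text is ambiguous; it does not clearly admit duplicates. But no sentence says one stay per patient, and the only definition of the index stay points to the hospitalization.

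A second reply is that a per-admission odds ratio is a legitimate target. That is so, but the plan does not declare it.

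Three stronger readings are tempting, and the documents do not support them.

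- *A reader might infer that survivors are counted many times while a patient who dies enters once.* A patient who dies in a later stay also contributes the earlier survived stays. The correct statement is at most one death row per patient. In the simulations with a true effect, crude mortality moved by −0.5 to +0.6 percentage points, so it is not always diluted.
- *A reader might infer that ignoring the correlation makes the confidence interval too narrow.* The naive and clustered standard errors were practically equal.
- *A reader might infer that the odds ratio is certainly biased, with false-positive rates of 40% or more.* Rates of 40–47% did occur at frailty SD 1.5 with 15,000 patients, return tied to the ratio and no covariate carrying frailty. None of those inputs is in the documents, and Section 6.2 adjusts for age, comorbidities and other factors that may absorb part of the frailty.

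**Conclusion.** The point holds as a specification gap with a conditional consequence. The plan does not settle whether the unit is the patient or the hospitalization, and it has no method for repeated patients if it is the latter.

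Harm requires three things together: return that depends on the ratio, a ratio that persists across stays, and frailty that the covariates miss. The effect on the estimate is then small, and the effect on the test depends heavily on sample size and on the strength of those links. If return is unrelated to the ratio, no material inflation is expected. The documents do not show which case applies. The change is still worth making, because the first-stay rule stayed close to nominal in every assumed setting and removes the ambiguity.

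**What to change.** Reword two criteria in Section 4:

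- Inclusion 2: *first eligible ICU admission per patient in the database*.
- Exclusion 7: *any later ICU admission of the same patient, in the same or a later hospitalization*.

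If the sponsor wants a per-admission estimand, say so in Sections 3 and 6.2, use patient-clustered standard errors for the repeated rows, and add the first-stay-per-patient analysis to Section 6.3, reported beside the main result. Clustered errors alone are not enough, because they do not remove the selection effect. In either case, give the number of patients and the number of stays in the flowchart promised in Section 8.

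The cost is two lines of wording, one line of extraction code and a somewhat smaller row count.

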6.4 Missing Data Handling

- Exclude patients missing primary exposure or outcome
- For covariates (SpO_2 , MAP, comorbidities):
 - If <5% missing: complete-case analysis
 - If >5% missing: consider multiple imputation

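### The objective speaks of critically ill adults, but only stays with a blood gas are analysed and no planned step assesses that selection

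*Combined protocol and SAP*

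**What the plan says.** The primary objective (section 2) asks whether the ratio "is independently associated with ICU mortality in critically ill adults". Section 3 gives the population as "Adult ICU patients (≥ 18 years) in MIMIC-II database". Neither statement mentions blood gas sampling.

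The restriction comes in section 4, where inclusion criterion 3 requires "At least one arterial blood gas measurement with PaO_2 and PaCO_2". Section 6.4 repeats it: "Exclude patients missing primary exposure or outcome". Section 3 describes the sampling as "Retrospective census of all eligible patients meeting inclusion/exclusion criteria". Section 5 sets the exposure time point as "First ABG per ICU stay (primary), or median/peak ABG values for sensitivity analysis".

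The primary model in section 6.2 adjusts for "SpO_2 , MAP, age, sex, ICU type, comorbidities". It has no severity score. Mechanical ventilation is among the adjustment covariates in section 5 but is missing from the section 6.2 list. The secondary objectives and section 6.3 do plan a subgroup analysis by "mechanical ventilation status".

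**The concern.** The analysed cohort is ICU adults in whom someone drew an ABG. The objective is wider than that, and a reader of the final report would naturally carry the conclusion over to all ICU adults.

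Two separate things are at stake.

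- **Generalisation.** If stays without an ABG differ in case mix or in how the ratio relates to death, the result need not carry over to them. The plan collects nothing that would let a reader judge this.
- **The estimate itself.** Suppose a patient is more likely to be sampled when gas exchange looks poor, and also when the patient looks ill for other reasons. Among sampled patients, a good ratio then tends to accompany more illness of another kind. If the model does not hold that illness, the adjusted odds ratio shifts. Section 6.2 judges independence by whether the ratio stays significant after adjustment, so a shift can alter the answer to the primary question.

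That ABGs are drawn on clinical concern is a reasonable inference. The documents do not say why they were drawn.

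**Working it through.** **Step 1. Does any planned step address the selection?**

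| Section | Content | Addresses ABG selection? |
|---|---|---|
| 6.1 | Baseline comparison across ratio quartiles | No: sampled stays only |
| 6.2 | Logistic model | No: sampled stays only |
| 6.3 | Subgroups; sensitivity to extreme values, DNR status, first versus median ABG | No: sampled stays only |
| 6.4 | Exclusion for missing exposure; imputation considered for covariates | No |
| 8 | Flowchart of included and excluded patients | Shows who was excluded, but plans no comparison |

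**Step 2. When would the odds ratio be distorted?** The documents give no sample size, mortality, sampled share or expected odds ratio, so there is no figure to reproduce. The inputs below are all assumptions.

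Set-up: 600,000 stays per scenario; X is the standardised ratio, C one measured covariate and U unmeasured severity, with X containing 0.3·C.

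- Death: logit P = −2.4 + b·X + 0.4·C + u·U, with b = ln 0.80 or 0
- Sampling: logit P = s0 + sx·X + sc·C + su·U, with s0 = −0.5, 0.5 or 2.0 (sampled share 39% to 85%)
- Fitted model: death on X and C, in all stays and then in sampled stays only

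| Sampling depends on | Sampled OR ÷ all-stay OR | Example |
|---|---|---|
| X and C only (sx −0.7, sc 0.7; no U) | 0.999–1.000 | 0.801 → 0.800 |
| U only, unrelated to X (su 1.0, u 0.7) | 0.998–1.002 | 0.808 → 0.810 |
| X, C and U, moderate (sx −0.7, sc 0.5, su 0.7, u 0.7) | 1.03–1.07 | 0.811 → 0.866 at 40% sampled |
| X, C and U, strong (sx −1.2, sc 0.5, su 1.2, u 1.0) | 1.09–1.22 | 0.824 → 0.984 at 42% sampled |

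The last two rows include runs with U independent of X and, for b = ln 0.80 in both rows and b = 0 in the strong row, runs with U correlated −0.3 with X. With no true effect and U independent of X, strong joint selection turned 0.996 into 1.195. The distortion shrinks as the share rises: in that strong null case it was 1.200 at 42% sampled and 1.095 at 80%.

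Monte Carlo error on a log odds ratio is roughly 1/√(600,000 × 0.10 × 0.90) = 0.004 in all stays and 1/√(240,000 × 0.10 × 0.90) = 0.007 at 40% sampled. The first two rows are therefore indistinguishable from no distortion.

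**Step 3. Is the direction known?** No. With 60% sampled, about 10% mortality and u = 0.85, reversing the sign of sampling on X moved the odds ratio from 0.81 to 0.74, away from 1.

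**Step 4. Would weighting repair it?** In the same setting, inverse-probability-of-sampling weights built on the measured covariate changed the sampled odds ratio from 0.866 to 0.870 (all-stay value 0.813), and in a stronger case from 0.909 to 0.918 (all-stay value 0.819). Conditional on covariates already in the model, such weights leave selection on U untouched.

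**The case against.** The strongest reply is that the ratio exists only where an ABG exists. The criterion is unavoidable, it is stated openly, and the census is expressly of eligible patients. This stands. Criterion 3 should stay, and the different handling of missing covariates in section 6.4 is not an inconsistency, because a patient without an ABG is ineligible rather than a cohort member with a missing value. It does not answer the point that the objective is worded more widely than the criterion.

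Second, clinicians do not know the ratio before the first ABG, so selection on it must work through correlates. SpO2 and MAP are among these and are already in the model. This stands in part: what remains after adjustment may be weaker than the coefficients assumed above. Severity and ventilation are still absent from section 6.2.

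Third, ordinary confounding by omitted severity could be the larger problem. With U correlated −0.3 with the ratio and a true conditional odds ratio of 0.80, the all-stay value in the moderate runs was already 0.646 to 0.648, and sampled stays gave 0.667 to 0.693, closer to 0.80. This also stands, so the all-stay odds ratio is not automatically the right benchmark.

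A reader might infer that selection definitely distorts the odds ratio, that it pulls a protective association toward 1 and could erase it, or that the result fails in critically ill adults. The documents support none of these. They give no sampled share, selection strength, sign or sample size, and failure to generalise is not shown.

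**Conclusion.** The mismatch between objective and cohort is established from the text, as is the absence of any planned step to assess it. Generalisation beyond ABG-sampled stays is unsupported, which is weaker than shown to be wrong.

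Distortion of the adjusted odds ratio is a conditional risk. It needs sampling to depend jointly on the ratio (or its correlates) and on predictors of death outside the model. The section 6.2 list leaves room for this. Under the assumed joint selection the sampled odds ratio was 3% to 22% above the all-stay value; with the sign reversed it was about 9% below (0.74/0.81 = 0.91). These figures illustrate a mechanism and are not estimates for this database. A high sampled share would make the issue small, which is why that share needs to be reported.

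**What to change.** 1. Restate the primary objective, the section 3 population and the conclusion as applying to adult ICU patients who had an ABG drawn.
2. Report the share, covariates and ICU mortality of otherwise eligible stays with and without an ABG. Define otherwise eligible by the criteria that do not refer to the ABG (age, index stay, SpO2 and MAP available, discharge status known), and take the covariates at a time that exists in both groups.
3. Add mechanical ventilation to the section 6.2 covariates, as section 5 already lists it. Repeat the primary model in ventilated stays as a selection sensitivity analysis if the table in item 2 shows that ABG sampling there is nearly universal. Its result then describes ventilated stays.
4. Optional: weights for the probability of having an ABG, built from age, sex, ICU type, ventilation, SpO2 and MAP. They may address effects that differ across those variables, but must be labelled as not correcting selection on unmeasured severity.

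The cost is a narrower claim, extraction of stays without an ABG from the same database, one table and one additional model. The optional weighting would widen the interval.
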